**Component 1: Subjective sleep quality**

Examine question #6, and assign scores as follows:

Response	Component 1 score
"Very good"	0
"Fairly good"	1
"Fairly bad"	2
"Very bad"	3

*Component 1 score:* \_\_\_\_\_

---

**Component 2: Sleep latency**

1. Examine question #2, and assign scores as follows:

Response	Score
≤15 minutes	0
16-30 minutes	1
31-60 minutes	2
> 60 minutes	3

*Question #2 score:* \_\_\_\_\_

2. Examine question #5a, and assign scores as follows:

Response	Score
Not during the past month	0
Less than once a week	1
Once or twice a week	2
Three or more times a week	3

*Question #5a score:* \_\_\_\_\_

3. Add #2 score and #5a score

*Sum of #2 and #5a:* \_\_\_\_\_

4. Assign component 2 score as follows:

Sum of #2 and #5a	Component 2 score
0	0
1-2	1
3-4	2
5-6	3

*Component 2 score:* \_\_\_\_\_

CONFIDENTIAL

This document is confidential. Do not disclose or use except as authorized.

**Component 3: Sleep duration**

Examine question #4, and assign scores as follows:

Response	Component 3 score
> 7 hours	0
6-7 hours	1
5-6 hours	2
< 5 hours	3

*Component 3 score:* \_\_\_\_\_

**Component 4: Habitual sleep efficiency**

1. Write the number of hours slept (question #4) here: \_\_\_\_\_

2. Calculate the number of hours spent in bed:

Getting up time (question #3): \_\_\_\_\_

Bedtime (question #1): \_\_\_\_\_

\_\_\_\_\_

*Number of hours spent in bed:* \_\_\_\_\_

3. Calculate habitual sleep efficiency as follows:

(Number of hours slept/Number of hours spent in bed) X 100 = Habitual sleep efficiency (%)

(\_\_\_\_\_ / \_\_\_\_\_) X 100 = %

4. Assign component 4 score as follows:

Habitual sleep efficiency %	Component 4 score
> 85%	0
75-84%	1
65-74%	2
< 65%	3

*Component 4 score:* \_\_\_\_\_

---

**Component 5: Step disturbances**

1. Examine questions #5b-5j, and assign scores for each question as follows:

Response	Score
Not during the past month	0
Less than once a week	1
Once or twice a week	2
Three or more times a week	3

*5b score:* \_\_\_\_\_

*5c score:* \_\_\_\_\_

*5d score:* \_\_\_\_\_

*5e score:* \_\_\_\_\_

*5f score:* \_\_\_\_\_

*5g score:* \_\_\_\_\_

*5h score:* \_\_\_\_\_

*5i score:* \_\_\_\_\_

*5j score:* \_\_\_\_\_

2. Add the scores for questions #5b-5j:

*Sum of #5b-5j:* \_\_\_\_\_

3. Assign component 5 score as follows:

Sum of #5b-5j	Component 5 score
0	0
1-9	1
10-18-4	2
19-27	3

*Component 5 score:* \_\_\_\_\_

---

**Component 6: Use of sleeping medication**

Examine question #7 and assign scores as follows:

Response	Component 6 score
Not during the past month	0
Less than once a week	1
Once or twice a week	2
Three or more times a week	3

*Component 6 score:* \_\_\_\_\_

---

**Component 7: Daytime dysfunction**

1. Examine question #8, and assign scores as follows:

Response	Score
Never	0
Once or twice	1
Once or twice each week	2
Three or more times each week	3

*Question #8 score:* \_\_\_\_\_

2. Examine question #9, and assign scores as follows:

Response	Score
No problem at all	0
Only a very slight problem	1
Somewhat of a problem	2
A very big problem	3

*Question #9 score:* \_\_\_\_\_

3. Add the scores for question #8 and #9:

*Sum of #8 and #9:* \_\_\_\_\_

4. Assign component 7 score as follows:

Sum of #8 and #9	Component 7 score
0	0
1-2	1
3-4	2
5-6	3

*Component 7 score:* \_\_\_\_\_

---

**Global PSQI Score**

[figure not shown]
Add the seven component scores together:

*Global PSQI Score:* \_\_\_\_\_

## **Appendix C**

### **EPIC -26**

**The  
Expanded  
Prostate  
Cancer  
Index  
Composite**

This questionnaire is designed to measure Quality of Life issues in patients with Prostate cancer. To help us get the most accurate measurement, it is important that you answer all questions honestly and completely.

Remember, as with all medical records, information contained within this survey will remain strictly confidential.

Today's Date (please enter date when survey completed): Month \_\_\_\_\_ Day \_\_\_\_\_ Year \_\_\_\_\_

Name (optional): \_\_\_\_\_

Date of Birth (optional): Month \_\_\_\_\_ Day \_\_\_\_\_ Year \_\_\_\_\_

Do Not  
Mark in  
This  
Space1. Over the **past 4 weeks**, how often have you leaked urine?

More than once a day..... 1  
 About once a day..... 2  
 More than once a week..... 3 (Circle one number)  
 About once a week..... 4  
 Rarely or never..... 5

23/

2. Which of the following best describes your urinary control **during the last 4 weeks**?

No urinary control whatsoever..... 1  
 Frequent dribbling..... 2 (Circle one number)  
 Occasional dribbling..... 3  
 Total control..... 4

26/

3. How many pads or adult diapers per day did you usually use to control leakage  
during the **last 4 weeks**?

None ..... 0  
 1 pad per day..... 1  
 2 pads per day..... 2 (Circle one number)  
 3 or more pads per day..... 3

27/

4. How big a problem, if any, has each of the following been for you **during the last 4 weeks**?

(Circle one number on each line)

	No Problem	Very Small Problem	Small Problem	Moderate Problem	Big Problem	
a. Dripping or leaking urine .....	0	1	2	3	4	28/
b. Pain or burning on urination.....	0	1	2	3	4	29/
c. Bleeding with urination.....	0	1	2	3	4	30/
d. Weak urine stream or incomplete emptying.....	0	1	2	3	4	31/
e. Need to urinate frequently during the day .....	0	1	2	3	4	33/

5. Overall, how big a problem has your urinary function been for you **during the last 4 weeks**?

No problem..... 1  
 Very small problem..... 2  
 Small problem..... 3 (Circle one number)  
 Moderate problem..... 4  
 Big problem..... 5

34/

## 6. How big a problem, if any, has each of the following been for you? (Circle one number on each line)

	No Problem	Very Small Problem	Small Problem	Moderate Problem	Big Problem	Do Not Mark in This Space
a. Urgency to have a bowel movement .....	0	1	2	3	4	49/
b. Increased frequency of bowel movements.....	0	1	2	3	4	50/
c. Losing control of your stools.....	0	1	2	3	4	52/
d. Bloody stools .....	0	1	2	3	4	53/
e. Abdominal/ Pelvic/Rectal pain...	0	1	2	3	4	54/

7. Overall, how big a problem have your bowel habits been for you **during the last 4 weeks?**

No problem.....	1					
Very small problem.....	2					
Small problem.....	3					55/
Moderate problem.....	4					
Big problem.....	5					

8. How would you rate each of the following **during the last 4 weeks?** (Circle one number on each line)

	Very Poor to None	Poor	Fair	Good	Very Good	
a. Your ability to have an erection?.....	1	2	3	4	5	57/
b. Your ability to reach orgasm (climax)?.....	1	2	3	4	5	58/

9. How would you describe the usual **QUALITY** of your erections **during the last 4 weeks?**

None at all.....	1					
Not firm enough for any sexual activity.....	2					
Firm enough for masturbation and foreplay only.....	3					59/
Firm enough for intercourse.....	4					

10. How would you describe the **FREQUENCY** of your erections **during the last 4 weeks?**

I NEVER had an erection when I wanted one.....	1					
I had an erection LESS THAN HALF the time I wanted one.....	2					
I had an erection ABOUT HALF the time I wanted one .....	3					60/
I had an erection MORE THAN HALF the time I wanted one.....	4					
I had an erection WHENEVER I wanted one.....	5					

Do Not  
Mark in  
This  
Space11. Overall, how would you rate your ability to function sexually **during the last 4 weeks?**

Very poor.....	1
Poor.....	2
Fair.....	3
Good.....	4
Very good.....	5

(Circle one number)

64/

12. Overall, how big a problem has your sexual function or lack of sexual function been for you  
**during the last 4 weeks?**

No problem.....	1
Very small problem.....	2
Small problem.....	3
Moderate problem.....	4
Big problem.....	5

(Circle one number)

68/

13. How big a problem **during the last 4 weeks**, if any, has each of the following been for you?  
(Circle one number on each line)

	No Problem	Very Small Problem	Small Problem	Moderate Problem	Big Problem	
a. Hot flashes.....	0	1	2	3	4	74/
b. Breast tenderness/enlargement..	0	1	2	3	4	75/
c. Feeling depressed.....	0	1	2	3	4	77/
d. Lack of energy.....	0	1	2	3	4	78/
e. Change in body weight.....	0	1	2	3	4	79/

THANK YOU VERY MUCH!!

**Appendix D:**

<https://ecog-acrin.org/resources/ecog-performance-status/>

ECOG PERFORMANCE STATUS*	
Grade	ECOG
0	Fully active, able to carry on all pre-disease performance without restriction
1	Restricted in physically strenuous activity but ambulatory and able to carry out work of a light or sedentary nature, e.g., light house work, office work
2	Ambulatory and capable of all self-care but unable to carry out any work activities. Up and about more than 50% of waking hours
3	Capable of only limited self-care, confined to bed or chair more than 50% of waking hours
4	Completely disabled. Cannot carry on any self-care. Totally confined to bed or chair
5	Dead

CONFIDENTIAL

This document is confidential. Do not disclose or use except as authorized

## Appendix E: Research Labs

Bone Metabolism Markers (should be drawn in AM and fasting)

**1. Collagen Type I C-telopeptide**

Serum; 1 ml; red top without serum separator; CPT4 code: 82523

**2. Bone Specific alkaline phosphatase**

Serum, 1 ml serum separator tube;

**3. Procollagen Type I Intact N terminal propeptide** Serum, 1 ml CPT code 83519

Hormone Metabolism Markers (should be drawn in AM and fasting)

**1. DHEA-S (also called DHEA-sulfate or dehydroepiandrosterone sulfate** Serum; .25 ml; serum separator tube; CPT4 code 80158

**2. Androstenedione**

Serum; 1 ml; red top tube without serum separator; CPT4 code 82157

**3. Testosterone**

Serum; 0.5 ml; serum separator tube

**4. Free testosterone**

Serum; 0.5ml. serum separator tube

**5. Estrone (precursor or estradiol which is also called estrogen)**

Serum; 2 ml. serum separator tube; CPT4 code 82679

**6. Estradiol (estrogen)**

Serum; 2 ml. serum separator tube; CPT4 code 84231

These tubes are to be drawn through their normal process for ordering blood work and should be sent to the clinical laboratory.

CONFIDENTIAL

This document is confidential. Do not disclose or use except as authorized

**Appendix F:**

Drugs to avoid because of interaction with CYP2C8 or CYP3A4 metabolic pathways

Gemfibrizil, carbamazepine, phenobarbital, pentobarbital, phenytoin, rifabutin, rifampin, rifapentine, nafcillin, modafinil, etavirenz, efavirenz, bosentan, cyclosporin, ergotamine, quinidine, sirolimus, tacrolimus, alfentanil, pimozide, St. John's Wort, ketoconazole, sertraline, digitoxin, haloperidol, ketamine, doxycycline, isoniazid, etravirine, dihydroergotamine and fentanyl.

Drugs to be used with caution

Warfarin (will likely require a change in warfarin dosing), omeprazole, midazolam, ciprofloxacin.

CONFIDENTIAL

This document is confidential. Do not disclose or use except as authorized

## Appendix G

Charts to calculate body fat %

### Chart (Men)

% Fat for Sum of Measurements at All 4 Locations

Sum in mm	Age 16-29	Age 30-49	Age 50+
20	8.1	12.1	12.5
22	9.2	13.2	13.9
24	10.2	14.2	15.1
26	11.2	15.2	16.3
28	12.1	16.1	17.4
30	12.9	16.9	18.5
35	14.7	18.7	20.8
40	16.3	20.3	22.8
45	17.7	21.8	24.7
50	19.0	23.0	26.3
55	20.2	24.2	27.8
60	21.2	25.3	29.1
65	22.2	26.3	30.4
70	23.2	27.2	31.5
75	24.0	28.0	32.6
80	24.8	28.8	33.7
85	25.6	29.6	34.6
90	26.3	30.3	35.5
95	27.0	31.0	36.5
100	27.6	31.7	37.3
110	28.8	32.9	38.8
120	29.9	34.0	40.2
130	31.0	35.0	41.5
140	31.9	36.0	42.8
150	32.8	36.8	43.9
160	33.6	37.7	45.0
170	34.4	38.5	46.0
180	35.2	39.2	47.0
190	35.9	39.9	47.9
200	36.5	40.6	48.8

CONFIDENTIAL

This document is confidential. Do not disclose or use except as authorized

## **Appendix H: Pill Diary**

**Study Participant** \_\_\_\_\_

**Self-Administration**

**Study Drug Diary**

**Dana-Farber/Harvard Cancer Center**

**Participant Identifier:** \_\_\_\_\_

**Protocol # : Enzalutamide with  
External Beam Radiation for Intermediate  
Risk Prostate Cancer:  
A Phase II study**

Your MD \_\_\_\_\_ Phone \_\_\_\_\_

Your RN \_\_\_\_\_ Phone \_\_\_\_\_

### **STUDY DRUG INSTRUCTIONS:**

**Study Drug:** Enzalutamide

**How Much:** Your dose is 160 mg

**How Often:** You will take 4 (40mg) capsules per day

**When:** You should take your capsules at the same time each day.

**SPECIAL INSTRUCTIONS: Do not make up missed or vomited doses if it has been longer than 12 hours since you were supposed to take your dose. Do not chew or crush capsules. Take with or without food. Bring in your Used pill bottles at each visit.**

Study Participant Initials \_\_\_\_\_ Date \_\_\_\_\_

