## 1. OBJECTIVES

### 1.1 Study Design

The goal of this exploratory study is to assess efficacy of adding enzalutamide in the neoadjuvant and adjuvant setting in combination with external beam radiation therapy (EBRT). The population will be prostate cancer patients with intermediate risk prostate cancer, choosing radiation therapy as their primary form of therapy. This is a phase II single arm trial that has as its primary objective to estimate the proportion of patients with PSA  $\leq 0.2$  ng/ml at the completion of therapy. This endpoint has been shown to be predictive of long term response in a similar risk-group of patients treated with radiation therapy and LHRH agonists. Secondary endpoints include measurement of serum hormone levels, health-related quality of life (HRQoL) and body fat measurements. It is expected that enzalutamide therapy in contrast to LHRH agonists has a much better profile for these secondary outcomes. Correlative studies will center on understanding enzalutamide's mechanism of action. Data from this trial, if convincing, would lead to a Phase III randomized trial comparing LHRH agonists to enzalutamide as neoadjuvant and adjuvant therapy in combination with EBRT.

On this study patients will be treated with 6 months of Xtandi (enzalutamide). Approximately one-third of the way through this treatment they will receive EBRT. Starting on Day 1, all patients will ingest enzalutamide **160 mg/day** at the same time each day without breaks (except as outlined for toxicity), with or without food, for 6 (28 day +/-3 days) cycles. Dose reduction of enzalutamide to 120 mg/day is allowed with the approval of the Medical Monitor, [name] (Section 6.2.2.3). Patients will be instructed to return all unused capsules at each study visit to assess compliance and will receive study drug every 28 days (+/-3 days) for 6 cycles (24 weeks).

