### **2.1.1 Previous Human Experience**

The tolerability, pharmacokinetics (PK), and antitumor activity of enzalutamide were studied in a multicenter, open-label, dose-escalation study of enzalutamide in 140 patients with advanced prostate cancer. Patients were treated with enzalutamide at doses of 30 to 600 mg/day until disease progression or intolerable side effects developed.

In this study, enzalutamide was absorbed rapidly after oral administration, with the median time to maximum plasma concentration ( $C_{max}$ ) after a single dose occurring at 1.00 hour (range 0.42 to 4.00 hours postdose). The PK of enzalutamide was essentially linear with no major deviations from dose proportionality in  $C_{max}$  or area under the curve values in the dose range of 30 to 600 mg. The terminal  $t_{1/2}$  for enzalutamide after a single dose was approximately 6 days (range 3 to 10 days) and did not appear to be affected by the dose size. In accordance with the long  $t_{1/2}$ , it took approximately 1 month after the start of a daily dose regimen to reach steady state. On achievement of steady state, the mean trough concentrations ( $C_{min}$ ) in individual patients remained constant for several months, suggesting time-linear PK. With daily oral administration of 150 mg/day, the mean accumulation index for enzalutamide was approximately 11, reflecting the long  $t_{1/2}$  relative to the dosing interval. Due to its slow clearance from plasma, the daily fluctuation in steady-state enzalutamide concentrations was low. The mean peak-to-trough ratios ( $C_{max}/C_{min}$ ) was 1.2 (range 1.14 to 1.3), indicating that variability in steady-state  $C_{max}$ ,  $C_{min}$ , and area under the curve values was low ( $\leq 30\% CV$ ). At 160 mg/day, the mean steady-state  $C_{min}$  is expected to be approximately  $12 \pm 4 \mu\text{g/mL}$ . Full PK profiles were linear and consistent over the dose range studied.

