Fatigue was the most frequently reported adverse event, with dose-dependent increases of Grade 3 fatigue (0% at 150 mg/day, 9% at 240 mg/day, 15% at 360 mg/day, and 20% at 480 mg/day). The dose of 240 mg/day was defined as the maximum tolerated dose. At doses of 240 mg and above, an increasing proportion of patients needed dose reductions for fatigue. Dose reductions were needed in 1 of 29 patients (3%) that received 240 mg/day, 3 of 28 patients (11%) that received 360 mg/day, and 5 of 22 patients (23%) that received 480 mg/day, and 0 of 58 patients that received 30, 60, or 150 mg/day. After dose reductions, the symptoms resolved. Only 1 patient discontinued treatment due to fatigue with an onset coinciding with prostate specific antigen (PSA) rise. Overall, the most common mild (grade 2) adverse events were fatigue ( $n = 38$  [27.1%]), nausea ( $n = 12$  [8.6%]), dyspnea ( $n = 11$  [7.9%]), anorexia ( $n = 8$  [5.7%]), and back pain ( $n = 8$  [5.7%]). Fatigue, nausea, and anorexia were the only mild adverse events with an increasing incidence as the dose of enzalutamide was increased. None of the grade 2 events required dose modification or the discontinuation of treatment, apart from 1 patient treated at 480 mg/day who had nausea at baseline and stopped therapy after 7 weeks.

CONFIDENTIAL

This document is confidential. Do not disclose or use except as authorized.

Version 13.0 Protocol Version Date: 1/09/2015

In the randomized clinical trial, 7 of 800 (0.9%) patients treated with enzalutamide 160 mg once daily experienced a seizure. No seizures occurred in patients treated with placebo. Seizures occurred from 31 to 603 days after initiation of enzalutamide. Patients experiencing seizure were permanently discontinued from therapy and all seizures resolved. There is no clinical trial experience re-administering enzalutamide to patients who experienced seizures.

The safety of enzalutamide in patients with predisposing factors for seizure is not known because these patients were excluded from the trial. These exclusion criteria included a history of seizure, underlying brain injury with loss of consciousness, transient ischemic attack within the past 12 months, cerebral vascular accident, brain metastases, brain arteriovenous malformation or the use of concomitant medications that may lower the seizure threshold.

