#### **5.2.2.3 Directions for Administration Enzalutamide**

Study participants will self-administer the total daily dose (160 mg) of enzalutamide as a single dose, once daily. Enzalutamide can be taken with or without food. Enzalutamide may be taken at any time during the day, but should be taken at the same time each day. A missed dose should be taken as soon it is remembered. If twelve or more hours have lapsed since their regularly scheduled time, patients should not take the missed dose; rather the patient should

CONFIDENTIAL

This document is confidential. Do not disclose or use except as authorized.

Version 13.0 Protocol Version Date: 1/09/2015

resume dosing at the next scheduled dose. Patients should not double up or take more than 1 dose of enzalutamide per day. Vomited doses should not be made up. Enzalutamide should not be crushed.

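### The pill diary in Appendix H makes the ban on retaking a vomited dose conditional on 12 hours; section 5.2.2.3 makes it unconditional

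*Combined protocol and SAP*

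**What the plan says.** Section 5.2.2.3 treats missed and vomited doses separately.

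- **Missed dose.** It is taken when remembered, up to a cut-off: "If twelve or more hours have lapsed since their regularly scheduled time, patients should not take the missed dose".
- **Vomited dose.** "Vomited doses should not be made up". No time condition is attached.
- **Daily limit.** "Patients should not double up or take more than 1 dose of enzalutamide per day".

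The Study Drug Instructions in Appendix H, which the participant initials and dates, put missed and vomited doses into one sentence with one condition: "Do not make up missed or vomited doses if it has been longer than 12 hours since you were supposed to take your dose". The same box gives the daily quantity, "You will take 4 (40mg) capsules per day", but says nothing further about vomiting and does not repeat the one-dose-per-day limit. No other section reconciles the two texts.

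**The concern.** Enzalutamide is self-administered at home, so the diary page is the instruction a man is likely to consult after he vomits. A ban limited to more than 12 hours is naturally read as leaving a retake open before then. A man who has just vomited may also feel that he has not really had his four capsules, so the daily quantity on the page need not stop him.

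If he retakes the dose, the study's own form has led him to depart from section 5.2.2.3. He has swallowed two doses in a day and will return four fewer capsules at a visit where returns are used to judge compliance. Vomiting is foreseeable: section 6.1.3 names nausea among the most common related events, and section 6.2.2.3 has a rule for severe vomiting. The documents give no vomiting rate, so the frequency of a retake cannot be estimated.

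**Working it through.** **Step 1. Compare the two instructions case by case.** Time runs from the scheduled dose.

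| Case | Section 5.2.2.3 | Diary, Appendix H | Agree? |
|---|---|---|---|
| Vomited, 12 h or less | Not made up | Not forbidden; retake implied | No |
| Vomited, more than 12 h | Not made up | Not made up | Yes |
| Missed, under 12 h | Taken | Not forbidden | Yes |
| Missed, exactly 12 h | Not taken | Not forbidden | No, trivially |
| Missed, more than 12 h | Not taken | Not made up | Yes |

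The first row is the point. The fourth concerns a single instant.

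**Step 2. Size of one retake in capsules.** 2 × 4 capsules × 40 mg = 320 mg swallowed, against 4 × 40 mg = 160 mg. Returned capsules fall by 4.

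**Step 3. Size in exposure.** The plan states no figure for this, so there is none to reproduce. The input comes from section 2.1.1: "With daily oral administration of 150 mg/day, the mean accumulation index for enzalutamide was approximately 11". Assumptions: the index R = 11 also holds at 160 mg; kinetics are linear, as section 2.1.1 describes; and the extra dose is fully absorbed with nothing lost from the first. The last assumption makes the results upper bounds. The unit is one day's exposure at steady state.

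- Share eliminated per day = 1/R = 1/11 = 0.0909. Daily retention r = 10/11 = 0.909.
- Extra exposure on the first day = 1/11 = 9.1%. On day 7 it is 0.0909 × 0.909^6 = 5.1%, and on day 28 it is 0.0909 × 0.909^27 = 0.7%.
- Total extra exposure from one retake = at most 1 steady-state day.
- Cycle 1, while drug is still accumulating: baseline = sum of (1 − r^d) for d = 1 to 28 = 28 − 10 × (1 − r^28) = 28 − 10 × 0.931 = 18.7 steady-state days. A retake on day 1 adds 1 − r^28 = 0.93 within the cycle. 0.93/18.7 = 5.0%.
- A later cycle: at most 1/28 = 3.6%. In cycle 2, where the baseline is 27.4 days, a day-1 retake gives 0.93/27.4 = 3.4%, inside that bound.
- The course of 6 × 28 = 168 days: baseline = 168 − 10 = 158 steady-state days. 1/158 = 0.63%.

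**Step 4. Sensitivity to half-life.** Section 2.1.1 gives a range of 3 to 10 days. With r = 2^(−1/t½), the same formulas give:

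| Half-life | First day, 1 − r | Cycle 1, day-1 retake | Course |
|---|---|---|---|
| 3 days | 20.6% | 0.998/24.2 = 4.1% | 1/164.2 = 0.61% |
| 10 days | 6.7% | 0.856/16.1 = 5.3% | 1/154.1 = 0.65% |

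The first-day figure of 9% therefore belongs to the mean index; across individual half-lives it runs from about 7% to 21%. The cycle and course figures barely move.

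**The case against.** The best defence is that the diary contains only a prohibition. It never tells a man to repeat a vomited dose, and its line on four capsules a day is a daily quantity that a literal reader could take as a limit. This stands in part: the permission is an inference. But the condition qualifies vomited doses as directly as missed ones, and the daily-quantity line does not say whether a vomited dose counts.

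The harm is also slight. Some or all of the first dose may be lost, steady state does not shift, and the primary endpoint is a PSA threshold after six cycles. All of that stands.

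A reader might infer more than the documents support in three places.

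- **Overdose.** Section 2.1.1 says "The dose of 240 mg/day was defined as the maximum tolerated dose", and 320 mg exceeds it. That limit concerns continued daily dosing, and the same study dosed daily up to 600 mg. One 320 mg day is a different exposure, as the figures above show, so the limit is no evidence of harm here.
- **Corrupted compliance data.** Section 1.1 says "Patients will be instructed to return all unused capsules at each study visit to assess compliance". But the diary log records date, time and amount for each dose, and the staff section compares capsules dispensed, returned and due, with room for discrepancy notes. A retake would appear as a four-capsule shortfall that the log can explain if the man records it. Section 13 plans no adherence analysis that it could distort.
- **A second conflict over missed doses.** The wording does differ, but only at exactly 12 hours, with no practical consequence.

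**Conclusion.** The inconsistency is real and minor. The diary makes conditional a ban that section 5.2.2.3 states without condition, and nothing reconciles them. Confidence is high for the mismatch of texts. It does not extend to how often men would act on it, which the documents give no means to estimate.

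Per retake, the consequence is 8 capsules in a day instead of 4 and a brief rise in exposure. The rise is at most about 9% of a steady-state day at first, about 5% of cycle 1 or 3.6% of a later cycle, and about 0.6% of the course. These bounds rest on linear kinetics, full absorption of both doses and a mean accumulation index of 11 carried from 150 to 160 mg/day. Sample size, decision rule and primary PSA analysis are untouched. This is a desirable correction and no threat to the trial's conclusions.

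**What to change.** Let section 5.2.2.3 govern and replace the diary sentence with:

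*If you vomit a dose, do not take it again. Take a missed dose only if it is less than 12 hours late. Never take more than one dose in a day.*

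This restores the unconditional rule on vomited doses, puts the one-dose limit on the page the participant uses, and aligns the missed-dose cut-off at exactly 12 hours.

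Appendix H is part of the protocol, so under section 12.1 the change goes in as an amendment, with IRB approval before use and notice to participating investigators. Diaries already issued would need replacing. Design, endpoints and analysis do not change.
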